6.4.11 PARTICIPANT DIARY CARD (PDC) SUBJECT SELF EVALUATION

Subjects will be provided and trained on a PDC and w 1 be asked to record the following the evening of study treatment through Day 6:

- Oral temperature and time taken (before 11:59 pm)
- General symptoms of feeling unwell
- Pain and itching at injection site
- Measure redness, swelling, bruising at injection site
- Medications taken

The completed PDC will be reviewed with the subject by the study staff at the 8 -14 day post-dose phone call and at the next in-person visit.

The study staff will review the PDC for general r mptoms (e.g. malaise, fatigue, headache, nausea, and myalgia/arthralgia), injection site reaction symptoms (e.g. pain, erythema and edema), medical events and medications.

Any PDC entry determined to meet the CTCAE criteria for a Grade 1 or higher adverse event should be documented as an adverse ev nt wless deemed part of the subject's ongoing medical history. If the PDC entry does not meet the criteria o `a Grade 1 or higher AE as per the CTCAE guidelines, clinical judgment can be used to determine whether the entry should be recorded as an AE and documented accordingly in the site's source. For cases where the PDC entry and final AE reporting (i.e. grading) do not agree, the reasoning should be recorded in the source documents.

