6.8 ASSESSMENT OF CLINICAL STUDY ADVERSE EVENTS

The injection site will be assessed by study person el prior to and of at least 30 minutes after each study treatment and at 2 to 4 weeks post study treatment visits. They will also be advised to record local and systemic AEs for 7 days on a PDC. An adver e event assessment will be conducted at each visit during which subjects will be q eried regarding the occurrence of any adverse events, concomitant medications new onset illness or disease, as well as contraceptive compliance. Subjects will be reminded to contact study personnel and immediately report any event that happens for the duration of the study. Unsolicited adverse events will be captured f m the time of the informed consent to study discharge. These events will be recorded on the subject's CRF.

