8.5.3 SAFETY ANALYSES

All AEs will be summarized among the safety population by frequency per treatment arm. These frequencies will be presented overall and separatel, by dose, and will depict overall, by system organ class and by preferred term, the percentage of subjects affected. dditional frequencies will be presented with respect to maximum severity and to strongest relationship to Study Treatment. Multiple occurrences of the same AE will be counted only once following a worst-case approach with respect to severity and relationship to Study Treatment. All serious AEs will also be summarized as above.

The main summary of safety data will be based on events occurring within 14 days of any dose. For this summary, the frequency of preferred term events will be compared between study arms with risk differences and 95% confidence intervals, using the method of Miettinen and Nurminen [17]. As this analysis will use many event categories, and produce many confidence intervals, caution should be exercised when interpreting these confidence intervals. Separate summaries will be based on events occurring within 7 days of any dose and regardless of when they occurred.

For AE data, partial start dates x ll be imputed to the date of treatment to conservatively report the event as treatment-emergent, whenever the portion of the date is consistent with that of the Study Treatment. Otherwise, it will be imputed to th reliest date consistent with the partial date. A completely missing onset date will be imputed as the day of treatment. Partial stop dates will be assumed to be the latest possible day consistent with the partial date.

AE duration will be calculated as (Stop Date – Start Date) + 1.

Analyses and summaries will be performed on biomarker-positive subjects and on all subjects regardless of biomarker status separately.

8.5.4 **DISPOSITION**

Disposition will be summarized by treatment arm for the ITT population and will include the number and percentage randomized, the number and percentage who received each dose and the number who completed the trial. The number and percentage of subjects who discontinued will be summarized overall and by

Version Date: 01Jun2022

CONFIDENTIAL

Version 4.1

Page 74 of 87

reason. The number in each analysis population will also be presented. Summaries will be performed on biomarker-positive subjects and on all subjects regardless of biomarker status separately.

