4.3.4. Safety

The safety analysis population includes all subjects who receive at least one dose of Study Treatment. Subjects will be analyzed as to the treatment actually received.

4.4.Report Conventions

The following reporting conventions apply generally to tables, listings, and figures:

- Data from all study centers will be combined for analysis;
- P-values will be rounded to 3 decimal places. P-values that round to 0.000 will be presented as '<0.001' and p-values that round to 1.000 will be presented as '>0.999';
- Confidence intervals (CIs) will be presented as 2-sided 95% CIs unless specified differently for a given analysis;
- Summary statistics will consist of the number and percentage of subjects in each category for categorical variables, and the sample size, mean, standard deviation (SD), median, minimum, and maximum for continuous variables;
- Unless otherwise specified, all mean and median values will be formatted to 1 more decimal place than the measured value, standard deviation values will be formatted to 2 more decimal places than the measured value, and minimum and maximum will be formatted to the same decimal place as the measured value;
- All percentages will be rounded to 1 decimal place. The number and percentage of responses will be presented in the form XX (XX.X);

- Unless otherwise specified, all analyses and summary tables will have the analysis population sample size (i.e., number of subjects), and displayed by the treatment arm and total;
- Subjects who received mixed treatments will not be included in the summaries of overall safety according to the assigned treatment arm; their data will be reported elsewhere.
- All collected data will be listed;
- SAS® Version 9.3 or higher will be the statistical software package used to produce all data summaries, listings, and statistical analyses.

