f. Based on HPV-16 and/or HPV-18 positive specimen at baseline. Subjects will be classified according to the presence/absence of HPV-16 and/or HPV-18 at baseline by each of the three anatomic locations.

8.2.Immunogenicity Analyses

Levels of serum anti-HPV-16 and anti-HPV-18 antibody concentrations and Interferon- γ ELISpot response magnitudes will be assessed from sera and PBMCs isolated from whole blood, respectively, collected at baseline, Week 15, and Week 36 visits. Flow Cytometry response magnitudes will be assessed from PBMCs isolated from whole blood collected at baseline and Week 15 visits.

All of the endpoints will be summarized as continuous variables at each visit. Increases from baseline for each post baseline visit from ELISpot and Flow Cytometry, and titers for each post baseline visit from ELISA will be compared between treatment arms. These comparisons will be analyzed with difference in medians and associated exact non-parametric 95% CIs.

The mITT population with at least one immunogenicity measurement will be used for these immunogenicity analyses. Analyses will be performed on the baseline biomarker-positive subjects and on all subjects (regardless of biomarker status) separately.

8.3.Exploratory Analysis

9. Safety Analysis

All safety summaries and analyses will be based on subjects in the safety analysis set. These summaries and analyses will be performed on the baseline biomarker-positive subjects and on all subjects (regardless of biomarker status) separately. Safety listings will flag all subjects who are baseline biomarker positive.

9.1.Adverse Events

A pretreatment event is defined as any event that occurs prior to administration of any study treatment; it does not necessarily have to have a causal relationship with study participation. A treatment emergent adverse event (TEAE) is defined as any event temporally associated with the use of a product whether or not considered related to the use of the product. Adverse event (AE) verbatim reported terms will be coded by SOC and PT using the latest version of MedDRA.

For the purpose of inclusion in AE summaries/analyses, incomplete start and stop dates will be imputed as follows:

Missing start dates will be handled as follows (where UK, UKN and UNKN indicate unknown or missing day, month and year respectively):

- UK-MMM-YYYY: if MMM and YYYY are the same as that of 1st dose, then impute to same date as 1st dose; otherwise impute to 01-MMM-YYYY;

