- DD-UNK-YYYY; if DD and YYYY are the same as that of 1st dose, then impute to same date as 1st dose; otherwise impute to DD-JAN-YYYY;
- DD-MMM-UNKN; if DD and MMM are the same as that of 1st dose, then impute to same date as 1st dose; otherwise impute to DD-MMM-YOSCR, where YOSCR is year subject was initially screened;
- UK-UKN-YYYY: if YYYY is the same as that of 1st dose, then impute to same date as 1st dose; otherwise impute to impute to 01-JAN-YYYY;
- UK-MMM-UNKN: if MMM is the same as that of 1st dose, then impute to same date as 1st dose; otherwise impute to 01-MMM-YOSCR, where YOSCR is year subject was initially screened;
- DD-UNK-UNKN: if DD is the same as that of 1st dose, then impute to same date as 1st dose; otherwise impute to impute to DD-JAN-YOSCR, where YOSCR is year subject was initially screened;
- UK-UKN- UNKN: impute to date of subject's 1st dose.

If the imputed start date is after the raw stop date, then the imputed start date will be set as the same as the stop date.

Missing stop dates will be handled as follows (where UK, UKN and UNKN indicate unknown or missing day, month and year respectively):

- UK-MMM-YYYY: impute to the last day of the month;
- DD-UNK-YYYY: impute to DD-DEC-YYYY;
- DD-MMM-UNKN: impute to DD-MMM-YOLV, where YOLV is year of subject's last study visit;
- UK-UKN-YYYY: impute to 31-DEC-YYYY;
- UK-MMM-UNKN: impute to LD-MMM-YOLV, where LD is the last day of MMM and YOLV is year of subject's last study visit;

- DD-UNK-UNKN: impute to DD-DEC-YOLV, where YOLV is year of subject's last study visit;
- UK-UKN- UNKN: impute to day of subject's last study visit.

If the imputed stop date is before the raw or imputed start date, then the imputed stop date will be set as the same as the start date.

AE duration will be calculated as (Stop Date – Start Date) + 1.

AE summary tables will include numbers and percentages of subjects experiencing at least one event by treatment arm. The following is a list of AE summary tables to be generated:

- Overview of AE, AE with onset within 28 days/7 days after study treatment
- TEAEs, TEAEs with onset within 28 days/7 days after study treatment by SOC and PT
- TEAEs, TEAEs with onset within 28 days/7 days after study treatment by Dose Number, SOC and PT
- TEAEs, TEAEs with onset within 28 days/7 days after study treatment by Dose Number, CTCAE Grade, SOC and PT
- Serious TEAEs by Dose Number, SOC and PT

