- TEAEs, TEAEs with onset within 28 days/7 days after study treatment by Dose Number, Relationship to IP and EP, SOC and PT
- Serious TEAEs, serious TEAEs with onset within 28 days/7 days after study treatment by Dose Number, Relationship to IP and EP, SOC and PT

• Grade >=3 TEAEs, Grade >=3 TEAEs with onset within 28 days/7 days after study treatment by Dose Number, SOC and PT

• Grade >=3 TEAEs, Grade >=3 TEAEs with onset within 28 days/7 days after study treatment by Dose Number, Relationship to IP and EP, SOC and PT

- TEAEs with Action of Study Treatment Held, TEAEs with Action of Study Treatment Held with onset within 28 days/7 days after study treatment by Dose Number, SOC and PT
- TEAEs with Action of Study Treatment Permanently Discontinued, TEAEs with Action of Study Treatment Permanently Discontinued with onset within 28 days/7 days after study treatment by Dose Number, SOC and PT

Additional AE/SAE summary tables may be added as appropriate.

A subject with 2 or more different adverse events within the same level of the MedDRA term and regimen will be counted only once in that level using the most extreme incident (most severe for the intensity analyses, and related for the relationship to study drug

analyses). For the AE with missing relationship to drug/procedure will be imputed as related. TEAEs by dose will be counted by the AE onset date not earlier than the date of treatment and earlier than the subsequent treatment for the first dose and second dose, and any AEs with onset date on or later than the third dose will all be counted to the third dose.

Data listings will be provided for AE, SAE, TEAE leading to treatment discontinuation, TEAE with CTCAE Grade >=3, TEAE with onset within 28 days/7 days after study treatment, and AEs resulting in death separately.

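### SAP 9.1 puts an AE with a missing onset year in the screening year, so 40–56% of such post-dose AEs are dated before first dose; low impact, cheaply fixed by bounding the imputed date

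*SAP*

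**What the plan says.** **SAP 9.1 (Adverse Events)** defines a pretreatment event as one that occurs before any study treatment. It then imputes incomplete onset dates for use in the AE summaries.

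- Day missing: "if MMM and YYYY are the same as that of 1st dose, then impute to same date as 1st dose; otherwise impute to 01-MMM-YYYY".
- Day and year missing: first dose if the month matches that of dose 1, "otherwise impute to 01-MMM-YOSCR, where YOSCR is year subject was initially screened". If only the year is missing, the known day and month are likewise placed in the screening year.
- Everything missing: the date of first dose.
- An imputed start later than the recorded stop date is moved back to the stop date. No rule moves a start forward.

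The tables that use these dates include "TEAEs, TEAEs with onset within 28 days/7 days after study treatment by Dose Number, SOC and PT". For dose attribution, "TEAEs by dose will be counted by the AE onset date not earlier than the date of treatment and earlier than the subsequent treatment"; everything from dose 3 onward goes to dose 3.

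**Protocol 8.5.3** says that partial start dates will "be imputed to the date of treatment to conservatively report the event as treatment-emergent, whenever the portion of the date is consistent" with the treatment date, and otherwise take the earliest consistent date. It bases the main safety summary on 14 days after any dose. Secondary endpoint 1a (both documents) and SAP 9.1.2 use 7 and 28 days. **SAP Section 11** records only a change to the medical-history summary.

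**Protocol 7.2** says that a condition with onset before consent is not an AE.

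**The concern.** A rule meant to be conservative should not move a post-dose event out of the treatment-emergent tables. The missing-year rule can do so, and it can give an onset date that cannot be true for an event recorded as an AE. It is also incoherent: an AE with no date information stays treatment-emergent, while one with a known month may become pretreatment.

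The dose-1-only comparison raises a second question. Three doses are given, and many AE tables are by dose or by 7- and 28-day window. An event soon after dose 3 with its day missing can be dated before dose 3, and so fall out of the window or be counted to dose 2. At stake are the completeness of the windowed tables and attribution to dose.

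**Working it through.** The documents give no count of partially dated AEs and no figure to reproduce.

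**Inputs.** Doses at Day 0, Week 4 and Week 12, i.e. days 0, 28 and 84 (SAP 3.3). AEs collected to Week 40, i.e. 40 × 7 = 280 days (protocol 7.12). Screening up to 10 weeks, i.e. 70 days, before dosing (protocol Table 1).

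**Assumptions.** First dose uniform over the calendar (1,461 consecutive dates enumerated), onset uniform over the stated range, visits on target dates, screening 7 to 70 days before dose 1.

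**1. Year missing.** A post-dose AE is dated too early when its true year is later than the screening year. The time from screening to onset is at most 70 + 280 = 350 days, so at most one year-end lies between. The chance is (screening gap + mean onset day) / 365.25, with mean onset day 280 / 2 = 140.

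- Gap 7 days: (7 + 140) / 365.25 = 40.2%.
- Gap 70 days: (70 + 140) / 365.25 = 57.5%.

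The match to the dose-1 month rescues a few. Enumerating the rule for month known, day and year missing gives **40.1% and 56.3%** dated before first dose. All of these are also before screening: true onset is at most 350 days after screening, so moving it back a year puts it at least 365 − 350 = 15 days before screening, and the first of the month is no later.

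Example: screening in September 2021, dose 1 on 10 October 2021, AE in March 2022. The SAP date is 1 March 2021.

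**2. Effect of a bound.** A calendar month cannot recur within 280 days of first dose. Requiring a date on or after first dose and no later than last visit therefore fixes the year, and no post-dose AE becomes pretreatment.

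**3. Day missing, dose 3, current rule.** Day 84 never shares a month with day 0, so the dose-1 match cannot apply.

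| Onset after dose 3 | Outside every 28-day window | Counted to dose 2 |
|---|---|---|
| 0–7 days | 83.4% | 85.2% |
| 8–28 days | 37.6% | 37.6% |
| 0–28 days | 50.2% | 50.7% |

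Example: doses on 10 January, 7 February and 4 April 2022, AE on 6 April. The SAP date is 1 April, before dose 3 and 53 days after dose 2.

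For dose 2 with onset 0–7 days, none leave the 28-day window at target dates, but 65.7% leave the 7-day table and 85.2% are counted to dose 1. No day-missing post-dose AE becomes pretreatment, so all stay in the whole-study TEAE tables.

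**4. Matching to all three doses (the earlier dose if two fit).** Day missing:

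| | Current | All doses |
|---|---|---|
| Onset days 0–112: 28-day error | 12.9% missed + 12.9% false = 25.8% | 0% missed + 23.9% false = 23.9% |
| Onset days 0–112: wrong dose | 26.1% | 24.2% |
| Onset days 0–112: 7-day error | 33.3% | 55.6% |
| Onset days 0–280: 28-day error | 15.6% | 14.9% |
| Onset days 0–280: wrong dose | 10.5% | 9.7% |
| Onset days 0–280: 7-day error | 13.8% | 22.8% |

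If onsets are counted only to day 28 after each dose (to the day before dose 2 for dose 1), the gain looks larger: 28-day misses fall from 17% to 0% and wrong-dose counts from 34% to 15%. That range omits days 29–55 after dose 2. There, matching to all doses puts 100% into a 28-day window (54% under the current rule) and counts 54% to dose 3 (0% under the current rule).

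**The case against.** **Few events are affected.** This stands. Subjects will "be asked to record the following the evening of study treatment through Day 6", calls follow 8–14 days after each dose, and protocol 6.8 says that an adverse "event assessment will be conducted at each visit during which subjects will be" asked about new events. After dose 3, both the call and the Week 15 visit fall within 28 days at target dates. An unknown year in a 40-week study should be rare. SAP 4.4 adds "All collected data will be listed", so nothing is hidden.

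**Protocol 7.2 concerns true onset, and SAP imputation serves only the summaries.** This is fair: no AE is deleted from the database. But those summaries decide whether an event is shown as treatment-emergent, and an imputed onset before screening contradicts the event's being recorded as an AE.

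**The dose-1-only comparison is a permissible reading.** This largely stands. A reader might infer from the 83% and 85% that the day-missing rule is an error to be corrected by matching every dose. The documents do not support that. Protocol 8.5.3 speaks of the date of treatment in the singular, and its stated aim is treatment-emergent status, which the SAP rule keeps for every day-missing post-dose AE. The first-of-month fallback is the protocol's own. Those two figures also apply to the first week, where the diary makes a missing day least likely. Over the dosing period, matching to all doses mainly exchanges balanced errors for over-counting.

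**The missing 14-day analysis.** A reader might infer that the main safety comparison was dropped. The SAP follows endpoint 1a as both documents state it, and its 28-day table includes every event dated within 14 days of a dose. What remains is an unrecorded change.

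**Conclusion.** The missing-year rule in SAP 9.1 is wrong as written and should be changed, with low impact. It dates 40–56% of month-known, year-missing post-dose AEs before first dose and before screening, against protocol 8.5.3's aim and less conservatively than the SAP treats a wholly missing date. The percentages apply only to AEs with that pattern and rest on uniform timing and a 7- to 70-day screening gap. The number of such AEs is unknown and probably small.

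The day-missing point is secondary. For dose 3, 38% (onset days 8–28) to 50% (days 0–28) is the more relevant loss from the 28-day windows. If 1–5% of dose-3 AEs lack the day (an assumption), this is 0.01 × 0.376 = 0.4% to 0.05 × 0.502 = 2.5% of them. It is a choice of convention that should be made visible.

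Nothing here supports a claim of bias between arms by design, because the same rule applies to both. The 14-day mismatch is documentation only.

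**What to change.** 1. **Missing year (correction).** In SAP 9.1, use the earliest date consistent with the known parts that is on or after first dose, bounded by last visit and stop date. If none fits, use the earliest consistent date on or after consent. Apply this to every pattern with the year missing.
2. **Transparency.** Flag imputed onsets in the listings, and footnote each 7- and 28-day table with the number of imputed-onset AEs in it.
3. **Dose matching (option).** If wanted, add a sensitivity table that matches day-missing onsets to all three doses. State that it removes missed events but raises false entries, most of all in the 7-day table.
4. **Documentation.** Reconcile protocol 8.5.3's 14-day window with endpoint 1a and SAP 9.1.2, and record the change in SAP Section 11. A supplementary 14-day table is optional.

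The cost is a few lines of SAP text, a small programming change, table footnotes, a Section 11 entry and a clarification of protocol 8.5.3. No new data are needed.

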9.1.1. Adverse Events of Special Interest

Adverse events of special interest (AESI) are the adverse events deemed related to VGX-3100/placebo delivered with CELLECTRATM 5PSP that require expedited communication from the Site to the Sponsor and meet any of the following criteria:

- Grade 3 or greater persistent administration site erythema, and/or inducation recorded ≥ 2 hours immediately after Study Treatment
- Grade 4 or greater persistent administration site pain, tenderness recorded \geq 2 hours immediately after Study Treatment
- Grade 3 or greater fever
- Grade 3 or greater systemic symptoms, including generalized pruritus

An AE summary table will include numbers and percentages of subjects experiencing at least one AESI by dose number, SOC and PT.

9.1.2. Incidence of Adverse Events

For the adverse events with onset date within 28 days after any dose, the frequency of SOC and PT events will be compared between study arms with risk differences and 95% confidence intervals, using the method of Miettinen and Nurminen [5]. As this analysis will use many event categories and produce many confidence intervals, caution should be exercised when interpreting these confidence intervals.

A similar analysis will be provided for adverse events within 7 days after any dose and for adverse events during the study after any dose.

